## Steps for Cumulative Probabilities and CIs:

- 1. Create 100 imputed datasets including time to loss of PASI 75 response for each patient using PROC MI.
- 2. Run PROC LIFETEST for each imputed data set and store estimates for the survivor function (SURVIVAL) and the associated standard errors (STDERR) in the data set OUTSURV.

run;

- 3. In a data step use the data set OUTSURV to calculate
  - 1. T SURVIVAL=log(-log(SURVIVAL))
  - 2. T\_STDERR= STDERR/(SURVIVAL\*log(SURVIVAL))

data outsurv1; set outsurv;

# T\_SURVIVAL=log(-log(SURVIVAL)); T\_STDERR= STDERR/(SURVIVAL\*log(SURVIVAL))

run;

4. Use the data set OUTSURV1 as input for PROC MIANALYZE to combine the results for T\_SURVIVAL and T\_STDERR based on the multiply imputed data sets. As we have two strata and different time intervals, we combine the estimates separately for each combination =strata \* time interval.

```
ods output ParameterEstimates=Survival_MI;
proc mianalyze data=outsurv1;
by combination;
modeleffects T_Survival;
stderr T_STDERR;
run;
```

5. Back-transform the combined survival estimates to the original scale and calculate the cumulative probabilities and associated CIs

```
data Survival_MI2;
set Survival_MI;
MI_survival=exp(-exp(Estimate));
LCL=(MI_survival)^exp(quantile('NORMAL',.975)*STDERR);
UCL=(MI_survival)^exp(-quantile('NORMAL',.975)*STDERR);
MI_cumulative= 1-MI_survival;
LCL_cum=1-UCL;
UCL_cum=1-LCL;
```

run;

**p-values from Log-rank and Wilcoxon tests:** Use transformed estimates for the Log-rank and Wilcoxon test statistics and their associated standard errors for each imputed data set using the Wilson-Hilferty transformation (Wilson & Hilferty, 1931; Goria, 1992) and combine the results using Rubin's rules (PROC MIANALYZE).

## Steps for p-values from Log-rank and Wilcoxon tests

- 1. Create 100 imputed datasets including time to loss of PASI 75 response for each patient using PROC MI.
- 2. Run PROC LIFETEST for each imputed data set and store estimates for the test statistics and the associated standard errors (STDERR) in the data set HOMTESTS.
- 3. Apply Wilson-Hilferty transformation to the Chi-square statistic and standardize the resulting normal variable as below e.g.;

```
DATA HOMTESTS1;
```

SET HOMTESTS;
CHI_VALUE_WH=((ChiSq/DF)**(1/3) - (1-2/(9*DF)))/SQRT(2/(9*DF));
$CHI\_STERR\_WH = 1.0;$
RUN;
4. Use the data set HOMTESTS1 as input for PROC MIANALYZE to combine the results for CHI_VALUE_WH and CHI_STERR_WH based on the multiply imputed data sets
ODS LISTING CLOSE;
ODS OUTPUT ParameterEstimates=logrank_mi;
PROC MIANALYZE data=logrank;
by comp;
modeleffects chi_value_wh;
stderr chi_sterr_wh;
RUN;
ODS OUTPUT ParameterEstimates=wilcox_mi;
PROC MIANALYZE data=wilcox;
by comp;
modeleffects chi_value_wh;
stderr chi_sterr_wh;
RUN;
ODS LISTING;

## 1.9.5 Secondary variables

Secondary variables are:

**PASI 50/75/90/100 and IGA mod 2011 0 or 1 response over time** in subjects who were PASI 75 responders at Week 52, over time for subjects who were re-treated after relapse with secukinumab 150 mg or 300 mg, and over time in subjects who were partial responders at Week 52.

Loss of PASI 75 response over time in subjects who were PASI 75 responders at Week 52

**Loss of IGA 0 or 1 response over time** in subjects who were PASI 75 responders as well as IGA 0 or 1 responders at Week 52

**PASI score over time** in subjects who were PASI 75 responders at Week 52, over time for subjects who were re-treated after relapse with secukinumab 150 mg or 300 mg, and over time in subjects who were partial responders at Week 52.

Novartis	Confidential	Page 46
RAP Module 3	9-Apr-2018 (1:15)	Secukinumab / AIN457A2302E1

**IGA mod 2011 score over time** in subjects who were PASI 75 responders at Week 52, over time for subjects who were re-treated after relapse with secukinumab 150 mg or 300 mg, and over time in subjects who were partial responders at Week 52.

**Relapse** in subjects who were PASI 75 responders at Week 52, over time for subjects who were re-treated after relapse with secukinumab 150 mg or 300 mg, and over time in subjects who were partial responders at Week 52.

**Rebound** in subjects who were PASI 75 responders at Week 52, over time for subjects who were re-treated after relapse with secukinumab 150 mg or 300 mg, and over time in subjects who were partial responders at Week 52.

**EQ-5D** in subjects who were PASI 75 responders at Week 52, over time for subjects who were re-treated after relapse with secukinumab 150 mg or 300 mg, and over time in subjects who were partial responders at Week 52.

**DLQI score as well as DLQI 0 or 1 achievement** in subjects who were PASI 75 responders at Week 52, over time for subjects who were re-treated after relapse with secukinumab 150 mg or 300 mg, and over time in subjects who were partial responders at Week 52.

## 1.9.6 Methods of analysis

## Final analysis

## PASI 50, PASI 75, PASI 90, PASI 100 and IGA 0 or 1 response over time

Descriptive statistics will be provided until the last visit. Summary statistics for PASI 50, PASI 75, PASI 90, PASI 100 and IGA 0 or 1 response by visit starting from Week 52 onwards will be presented in contingency tables and will include absolute and relative frequencies.

Confidence intervals for response rates will be derived as well based on the score method including continuity correction (Newcombe, 1998).

#### PASI score over time

Summary statistics will be provided for absolute PASI scores as well as for percent change from core baseline by visit starting from Week 52 onwards and treatment group. **IGA mod 2011 score over time** 

Summary statistics for the IGA mod 2011 score over time will be presented by visit starting from Week 52 onwards and treatment group in contingency tables.

### Relapse

Relapse will be analyzed analogously to loss of PASI 75 response in the follow-up period.

A listing of these subjects will also be provided.

#### Rebound

The number and percentage of subjects experiencing rebound during follow-up period will be presented by visit and treatment group.

## For subjects who were PASI 75 responders and randomized to RW period

#### PASI 50, PASI 75, PASI 90, PASI 100 and IGA 0 or 1 response over time

Descriptive statistics will be provided until the last visit. Summary statistics for PASI 50, PASI 75, PASI 90, PASI 100 and IGA 0 or 1 response by visit starting from Week 52 onwards will be presented in contingency tables and will include absolute and relative frequencies. Confidence intervals for response rates will be derived as well based on the score method including continuity correction (Newcombe, 1998).

For PASI 50, PASI 75, PASI 90, PASI 100 and IGA 0 or 1 response at each visit starting from Week 52 onwards during RW period, each secukinumab dose regimen will be compared to placebo (up to last visit with more than 5% of subjects in placebo group) by means of the stratified Cochran-Mantel-Haenszel-test as well as by means of a logistic regression model with treatment group, geographical region, body weight stratum at core, and core baseline PASI as effects.

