The **investigator** is only responsible for collecting the **components** or scoring signs and total regional area. PASI calculations, including changes over time will be done by Novartis via the PASI Score eCRF. At Week 52, the investigator or qualified designee should ensure that all the information required for the PASI calculation was entered into the PASI Score eCRF at Week 52 and that a PASI score is available prior to contacting IRT. The Investigator or qualified designee will enter the Week 52 PASI score into the IRT system at Week 52 before subject receives the study treatment.

Based on PASI at Week 52, a subject to be eligible must be either a PASI 75 responder or partial responder according to the definitions stated below:

- PASI 75 responders: subjects with PASI 75 response (subjects achieving  $\geq 75\%$  improvement [reduction] in PASI score compared to baseline of the core study) at Week 52
- Partial responders: subjects with PASI 50 response (subjects achieving  $\geq 50\%$  improvement [reduction] in PASI score compared to baseline of the core study, but not achieving a PASI 75 response) at Week 52

During the study, at each visit, the PASI score will be calculated and response will be classified according to the definitions from CHMP guidelines for psoriasis [CHMP/EWP/2454/ 02 2004](#)

- **PASI 75 response:** subjects achieving  $\geq 75\%$  improvement (reduction) in PASI score compared to baseline of the core study are defined as PASI 75 responders
- **PASI 50 response:** subjects achieving  $\geq 50\%$  improvement (reduction) in PASI score compared to baseline of the core study are defined as PASI 50 responders
- **PASI 90 response:** subjects achieving  $\geq 90\%$  improvement (reduction) in PASI score compared to baseline of the core study are defined as PASI 90 responders
- **PASI 100 response/remission:** complete clearing of psoriasis (PASI=0)
- **Relapse:** when the achieved maximal PASI improvement from baseline of core study is reduced by  $>50\%$

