### **9.5 Analysis of secondary variables**

#### **9.5.1 Efficacy variables**

##### **Subjects who were PASI 75 responders at Week 52**

##### **PASI 50, PASI 75, PASI 90, PASI 100 and IGA 0 or 1 response over time**

Summary statistics for PASI 50, PASI 75, PASI 90, PASI 100 and IGA 0 or 1 response by visit will be presented in contingency tables and will include absolute and relative frequencies. Confidence intervals for response rates will be derived as well based on the score method including continuity correction ([Newcombe, 1998](#)).

For PASI 50, PASI 75, PASI 90, PASI 100 and IGA 0 or 1 response at each visit, each secukinumab dose regimen will be compared to placebo (up to last visit with more than 5% of subjects in placebo group) by means of the stratified Cochran-Mantel-Haenszel-test as well as by means of a logistic regression model with treatment group, geographical region, body weight stratum, and baseline PASI as effects.

For PASI 50, PASI 75, PASI 90 and IGA 0 or 1 response the placebo-adjusted response rates including 95% confidence interval (based on normal approximation) will be derived by visit. Figures will be provided as well displaying estimates for responder rates by treatment including confidence intervals.

Subjects that were re-randomized at Week 52, hence who PASI 75 responder will be split into two subgroups based on the IGA 0 or 1 response at Week 52. For each of these subgroups summary statistics for PASI 50, PASI 75, PASI 90, PASI 100 and IGA 0 or 1 response by visit will be presented in contingency tables and will include absolute and relative frequencies.

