#### 1.5.3 Screening (extension), baseline and post-baseline definitions

*Screening* refers to any procedures (e.g., checking inclusion and exclusion criteria) performed prior to the date of first dose of study treatment (for safety analysis) or prior to the randomization date in extension (for efficacy analysis). Per protocol, subject informed consent must be obtained prior to performing any study related activity. The date of signing informed consent is the start date of screening period. Any assessment obtained during the screening period will be labeled screening assessment. Assessments made on Day 1 may occur before or after the randomization or the first dose in extension. Further information will be found in [RAP Module 8].

Baseline is defined with respect to core and extension as follows:

Core baseline:

For efficacy analyses, core baseline is the last assessment (including unscheduled visits) obtained before the randomization in core. All assessments obtained after randomization in core are considered as post-baseline unless otherwise specified.

For safety analyses, core baseline is the last assessment (including unscheduled visits) obtained before the first dose of study treatment in core. All assessments obtained after the first dose of study treatment in core are considered as post-baseline unless otherwise specified.

Of note, as core baseline measurements are already identified in the core studies, they can be readily used for the purpose of extension study.

Extension baseline:

For efficacy analyses, extension baseline is the last assessment (including unscheduled visits) obtained on or after Week 52 and before the randomization in extension. All assessments obtained after randomization in extension are considered as post-baseline unless otherwise specified.

For safety analyses, extension baseline is the last assessment (including unscheduled visits) obtained on or after Week 52 and before the first dose of study treatment in extension. All assessments obtained after the first dose of study treatment in extension are considered as post-baseline unless otherwise specified.

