In general, a baseline value refers to the last measurement made prior to administration of the first dose of study treatment. However, for patient reported outcomes (e.g. patient's assessment of PSA pain), lab, ECG, if no pre-treatment value exists a value recorded after first dose can also be used as baseline if it was collected on the same day as first dose.

For efficacy analyses, core baseline will be used for PASI and IGA related variables, such as PASI response, PASI score, et al. Extension baseline will be used for PRO variables.

For safety analyses, extension baseline will be used for all safety variables if not specified.

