For loss of PASI 75 response, between-treatment differences will be evaluated using a logrank test, stratified by geographical region and body weight stratum, to compare the survival functions between secukinumab treatment groups versus placebo. The hazard ratios for these comparisons for loss of PASI 75 response and their corresponding 95% confidence intervals will be computed using a stratified Cox proportional hazards regression model with treatment group, core study and baseline PASI of core study and baseline PASI of extension study as explanatory variable and stratified by geographical region and body weight stratum.

Kaplan-Meier estimates including 95% confidence intervals for cumulative rate of subjects losing PASI 75 response will be calculated for each treatment group.

The number of subjects with loss of PASI 75 response, number of subjects in the analysis set, estimate of cumulative rate during RW period, median event time, and its estimated standard

Novartis	Confidential	Page 37
RAP Module 3	9-Apr-2018 (1:15)	Secukinumab / AIN457A2302E1

error, as estimable will be provided for each treatment group. In addition, for pre-specified time intervals (e.g., 4-week intervals) the following will be presented:

[figure not shown]
- for each treatment group and time interval: subjects at risk, subjects with loss of PASI 75 response, subjects with loss of PASI 75 response divided by subjects at risk, cumulative subjects with event and cumulative event probability including 95% confidence interval.
- for treatment comparisons the log-rank test and Wilcoxon test as well as the hazard ratio derived via Cox regression.

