The imputed data are saved in data set <impdata>. The outcomes of interest, i.e. the loss of PASI 75 response will be calculated from change from baseline PASI scores. The day of visit at which the first occurrence of losing PASI 75 response will also be obtained. In the case of missing visits or visit dates the planned visit day will be used., e.g. as follows:

DATA <impdata2>; SET <impdata>; IF <change from baseline PASI week primary endpoint>/<baseline PASI>=0.75 THEN <PASI 75 response>=1; ELSE <PASI 75 response>=0; END; RUN;

The treatment differences for each imputed data set will then be evaluated by using Cox proportional hazards regression as described section 1.9.2. This analysis will be done by \_IMPUTATION\_ for each pairwise comparison as described in section 1.9.5. The data set should be sorted such that the control group comes last. E.g as follows:

```
ods table HazardRatios = hazardratios
proc phreg data = <impdata2>;
class <treatment group> <core study> <geographical region> <body weight stratum>
model TIME*PASI75(1)= <treatment group> <core study> <core baseline PASI> <extension baseline PASI>/ties=exact;
STRATA < geographical region> < body weight stratum>
by _Imputation ;
run:
      data dhazardratios:
            set hazardratios;
            where Description in ( 'TRT01PN 1 vs 3' 'TRT01PN 2 vs 4');
            if Description in ( 'TRT01PN 1 vs 3') then comp =1;
            else if Description in ('TRT01PN 2 vs 4') then comp =2;
            if HazardRatio NE . and HazardRatio > 0 then ESTIMATE=log(HazardRatio);
            if WaldLower NE . and HazardRatio > 0 then STDERR=log(WaldLower/HazardRatio)/-probit(1-0.05/2);
            if missing(ESTIMATE) or missing(STDERR) then delete;
     effect="LogHR";
      run;
```

• The PHREG procedure and following MIANALYZE procedure could then be run with by-variables for the comparison and response identifier.

The MIANALYZE procedure expects the parameter estimate in the variables ESTIMATE, and the corresponding standard error in the variable STDERR. The dataset dhazardratios above contained the estimate and its standard error for log(Hazard ratio)

The estimates and standard errors of the log of hazard ratio based on the 100 imputed data are then combined by applying Rubin's rules for multiple imputed data sets, see Little and Rubin (2002).

The SAS procedure MIANALYZE will be applied as follows:

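### The by-visit logistic models against placebo leave out Week 52 PASI, which the Cox model already uses; if that value is prognostic, this costs a modest amount of power, and the between-arm tests should start at Week 56

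*SAP*

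**What the plan says.** SAP 1.9.6, for PASI 75 responders randomized to the withdrawal period, compares each dose with placebo at every visit from Week 52 on. It uses a stratified Cochran-Mantel-Haenszel test and a "logistic regression model with treatment group, geographical region, body weight stratum at core, and core baseline PASI as effects". Testing continues to the last visit at which more than 5% of placebo subjects remain.

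Protocol 9.5.1 describes the same model as a "logistic regression model with treatment group, geographical region, body weight stratum, and baseline PASI as effects". It has one PASI term and does not say which baseline is meant.

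The Cox model for loss of PASI 75 in the same subjects (SAP 1.9.2) has "treatment group, core study and baseline PASI of core study and baseline PASI of extension study as explanatory variable", stratified by region and weight. The code in SAP 1.9.4.2 agrees: "model TIME*PASI75(1)= <treatment group> <core study> <core baseline PASI> <extension baseline PASI>/ties=exact".

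Two definitions matter. For efficacy, SAP 1.5.3 says that "extension baseline is the last assessment (including unscheduled visits) obtained on or after Week 52 and before the randomization in extension". The same section says that "core baseline will be used for PASI and IGA related variables, such as PASI response, PASI score, et al".

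**The concern.** Everyone in this comparison was selected on PASI response at Week 52. How far a subject then stands from each response threshold plausibly depends on the residual PASI at that visit, and less on the PASI measured a year before, ahead of any treatment. The Cox model takes account of this and the by-visit logistic models do not. No reason is given for the difference.

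Response over time against placebo is the first secondary objective in Protocol 2.2. If Week 52 PASI predicts later response, the treatment test in these models has less power than the collected data allow.

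The same sentence also starts the between-arm comparison at Week 52. That visit precedes randomized treatment, and PASI 50 and PASI 75 response there are fixed by the entry rule.

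**Working it through.** **1. Is the covariate admissible and available?** Yes. By SAP 1.5.3 the extension baseline is taken before re-randomization. Protocol 6.4.2 requires at Week 52 that "a PASI score is available prior to contacting IRT", so the value should exist for essentially every randomized subject. The SAP 1.5.3 rule on core baseline fixes the reference from which PASI and IGA response are derived. It does not bar a covariate, and the Cox model carries both PASI values under the same rule.

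**2. The plan's own power figure.** The documents give no power or precision figure for the logistic models. The figure they do give (Protocol 9.7, SAP 1.11) is more than 90% power for the log-rank test with about 400 subjects per dose at 2:1, 10% v 23% loss of PASI 75, and one-sided 2.5%.

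- Hazard ratio = ln(0.90)/ln(0.77) = 0.403.
- Expected events = 133.3 × 0.23 + 266.7 × 0.10 = 57.3.
- Schoenfeld: |ln 0.403| × √(57.3 × 2/3 × 1/3) − 1.96 = 3.24 − 1.96 = 1.28, so power is 90.0%.
- Freedman gives 94.3%, and a two-proportion test gives 91.9%.

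The stated figure reproduces.

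**3. Effect of adding Week 52 PASI.** Simulation of 3,000 trials per setting, with 276 v 138 subjects as planned. The logistic model had treatment, three regions, weight stratum and core PASI, fitted with and without Week 52 PASI. Tests were two-sided 5%, the SAP 1.1 default.

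The assumptions below are not in the documents:

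- core PASI has mean 22;
- Week 52 PASI is 0 to 25% of core PASI, with correlation about 0.39 between the two;
- the prognostic odds ratio is 1 to 4 per SD of Week 52 PASI.

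At 90% v 77% response (the complement of the planned 10% v 23% loss), each arrow runs from without to with Week 52 PASI:

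| Odds ratio per SD | log-OR | SE of log-OR | mean z | power (%) | SE of standardised risk difference | relative efficiency |
|---|---|---|---|---|---|---|
| 1 | 0.998→1.001 | +0.3% | 3.42→3.42 | 92.8→93.0 | +0.1% | 1.00 |
| 1.5 | 1.014→1.045 | +1.9% | 3.46→3.50 | 93.4→93.9 | −0.9% | 1.02 |
| 2 | 1.014→1.101 | +5.3% | 3.44→3.54 | 92.6→94.2 | −3.9% | 1.08 |
| 3 | 1.055→1.278 | +12.8% | 3.53→3.78 | 94.7→97.1 | −8.6% | 1.20 |
| 4 | 1.072→1.430 | +20.0% | 3.54→3.93 | 94.9→98.7 | −12.4% | 1.30 |

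At a smaller contrast of 70% v 60% (assumed), power moved from 53.2 to 52.9% (odds ratio 1), 54.6 to 58.3% (2) and 53.3 to 65.4% (4).

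The odds ratio is non-collapsible. Adding a prognostic term raises the standard error of its log but moves the estimate further from zero by more, so z rises. On the scale of a standardised risk difference the standard error falls.

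**4. Sparse visits.** The 5% rule lets testing continue down to about 0.05 × 138 ≈ 7 placebo subjects. With 200 v 20 subjects, the average fitted standard error of the log-OR ran into the thousands both with and without the extra term. That is separation, present under either model.

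**5. The Week 52 visit.** Entry to the withdrawal period requires PASI 75 response at Week 52. Apart from subjects randomized in error, whom SAP 1.2 keeps, PASI 50 and PASI 75 response are 100% in every arm, so no treatment effect can be estimated. PASI 90, PASI 100 and IGA 0 or 1 can vary at that visit, but a between-arm test before randomized treatment says nothing about treatment. A model with both PASI values would also be degenerate there, because together they determine PASI response.

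**The case against.** A reader might infer that the plan gives wider confidence intervals for the reported odds ratios than it needs to. It does not: the log-OR standard error rises by 0.3% to 20% when the term is added. The fuller model also estimates a different conditional odds ratio, so the change is not purely one of efficiency.

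A reader might also take power at one-sided 1.25% as the yardstick. That level belongs to H1 and H2. The by-visit responses are outside the testing strategy (SAP 1.9.3), and at two-sided 5% the planned contrast already has about 93 to 95% power.

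Nor do the documents show that the SAP narrowed a broader protocol model. Protocol 9.5.1 lists one PASI term too; the SAP only says which baseline. A hazard of first loss and the odds of response at a visit are different quantities, so unequal covariate sets are not an error in themselves. Randomization protects each comparison, a Cochran-Mantel-Haenszel test runs alongside, and loss of PASI 75 is already analysed with Week 52 PASI.

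Timing is the strongest practical objection. SAP 1.1 describes these as re-run analyses, and Protocol 5.4 has designated sponsor staff unblinded after all subjects complete Week 68. Replacing the model at that stage would break comparability with previously conducted runs and invite questions about choice of model.

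All of this stands. It limits the point to power and to a standardised risk difference, and argues for adding a model and not replacing one. It does not supply a reason for the omission or for testing at Week 52.

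**Conclusion.** The by-visit logistic models omit a pre-randomization value that is already collected and already used in the Cox model. If Week 52 PASI is prognostic among these responders, the omission costs power for the treatment test and precision of a standardised risk difference. Over assumed odds ratios of 1 to 4 per SD, the gain from adding it is about 0 to 4 percentage points of power at 90% v 77% and about 0 to 12 at 70% v 60%. The variance gain for the risk difference is a factor of 1.00 to 1.30. If the value is not prognostic, the gain is nil. The prognostic strength, the PASI distributions and the 70% v 60% contrast are assumptions.

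The documents do not support reading this as bias, as lost precision of the odds ratio, or as a threat to the primary result: the primary log-rank test does not adjust for PASI at all. The Week 52 point needs no assumption about prognosis. Priority is low.

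**What to change.** In SAP 1.9.6, for visits from Week 56 onwards:

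- Add extension-baseline (Week 52) PASI to the logistic models for PASI 50/75/90/100 and IGA 0 or 1, to match SAP 1.9.2. Add core study as well where the data are not sparse; the simulation did not test that term.
- Keep the existing model alongside, and record the addition in SAP 1.1.1 as a change.
- State that the two models estimate different conditional odds ratios.
- If precision is the aim, report a standardised risk difference. This sits naturally beside the placebo-adjusted response rates in Protocol 9.5.1.
- Start the between-arm tests at Week 56. Week 52 can remain as a descriptive row.

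The cost is one or two extra model terms, a second set of estimates to explain, and possible separation at late visits with few placebo subjects, where the present model already has that problem. No new data are needed, and moving the start of testing to Week 56 costs nothing.
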